5.4.1.4 Sensitivity analyses

We will conduct sensitivity analyses around attack definitions including:

- In our definition of attacks, we considered on-demand therapy administrations by a healthcare professional, ED visits, and inpatient hospitalizations occurring within *five*

days of each other to be considered part of a single attack. We will vary this duration in sensitivity analysis to determine how this impacts attack rates.

- In our definition of non-severe attacks, we assume that patients will have on-demand treatment on hand to treat up to 2 attacks, which is based on treatment guideline recommendations. In sensitivity analysis, we will estimate the number of attacks treated by self-administration without subtracting out two doses to represent drug on-hand.

5.4.1.5 Limitations

There are a number of limitations associated with the proposed analysis:

- The Optum Clinformatics ® Data Mart, which includes over 67 million patients, does not include *all* US patients. The data also represents the policies of the included health plans and might not be representative of *all* US based HAE health plan policies. However, no US based real-world data set reflects all US patients or health plan policies. The Optum Clinformatics ® Data Mart was selected because of its wide patient coverage and availability of criteria (e.g., exposure, outcomes) necessary to complete the analysis.
- There are currently no validated algorithms for measuring attack rates in claims data. We took guidance from clinical experts, treatment guidelines, and published literature for defining severe and non-severe HAE attacks. Please refer to the Model Analysis Plan (MAP) for criteria around use of attack estimates in the model.

Annex 1: HAE drugs

Generic	Brand (Administration)	Acute Attack Dose	Long-Term Prophylaxis Dose	How Supplied
C1 Inhibitor, Human (plasma derived C1 inhibitor [pdC1INH])	Cinryze* (IV)	Adults† 1,000 units once. Additional 1,000 units IV if no improvement 60 minutes after first dose. (not studied in children)	Adults & Children ≥12 years 1,000 units every 3-4 days Max Dose: 2,500 units or 100 units/kg every 3 days Children (6-11 years) 500 units every 3-4 days Max Dose: 1,000 units every 3 days Short-Term Prophylaxis† (before a procedure) 20 units/kg or 1,000 units immediately prior to procedure	Cinryze 500 units Powder Vial Reconstitute with 5mL SWFI Concentration: 100 units/mL
	Haegarda* (SC)		Adults & Children ≥6 years 60 IU/kg twice weekly (every 3-4 days)	Haegarda 2000 IU Powder Vial Reconstitute with 4mL SWFI Concentration: 500 IU/mL Haegarda 3000 IU Powder Vial Reconstitute with 6mL SWFI Concentration: 500 IU/mL
	Berinert* (IV)	Adults & Children ≥6 year 20 IU/kg once		Berinert 500 IU Power Vial Reconstitute with 10mL SWFI Concentration: 50 IU/mL

Generic	Brand (Administration)	Acute Attack Dose	Long-Term Prophylaxis Dose	How Supplied
Lanadelumab	Takhzyro* (SC)		Adults & Children ≥12 years 300mg every 2 weeks. After 6 months, reduce to every 4-week dosing if patient well-controlled.	Takhzyro 300mg/2mL Solution Vial Concentration: 150mg/mL
C1 Esterase Inhibitor, Recombinant (recombinant human C1 inhibitor [rhC1INH])	Ruconest* (IV)	Adults & Children ≥13 years (non-laryngeal attacks) 50 IU/kg/dose Max Dose: 4,200 IU/dose; 8400 IU per 24 hours	Adults & Children ≥13 years† 50 IU/kg/dose once or twice weekly Max Dose: 4,200 IU/dose once or twice weekly Short-Term Prophylaxis† (before a procedure) 50 IU/kg or 1,000 units immediately prior to procedure	Ruconest 2100 IU Powder Vial Reconstitute with 14mL SWFI Concentration: 150 IU/mL
Ecallantide	Kalbitor* (SC)	Adults & Children ≥12 years 30mg once (administered as three injections of 10mg) Max Dose: 60mg in 24 hours		Kalbitor 10mg/mL Vial Solution for Injection (3 vials per package)
Icatibant	Firazyr (SC)	Adults 30mg once. Repeat administrations in 6-hour intervals. Max Dose: 90mg in 24 hours (EU Pediatric Dosing Weight Based)		Firazyr 30mg/3mL Solution Vial Icatibant 30mg/3mL Solution Prefilled Syringe
Berotrastat	Orladeyo* (Oral)		Adults & Children ≥12 years 150 mg once daily. Adjustment: 110mg once daily for hepatic impairment or GI reactions.	Orladeyo 110mg Capsule Orladeyo 150mg Capsule

Generic	Brand (Administration)	Acute Attack Dose	Long-Term Prophylaxis Dose	How Supplied
Danazol	Danocrine (Oral)		
Adults 200 mg twice or three times daily. 100mg every other day also possible. If favorable response after 1-3 months, reduce dose by half. Max Dose: 600mg/day
 
Children >16 years Initially 2.5mg/kg/day (max initial dose: 50mg/day) for ~2 weeks. Then triturate to max tolerated dose and reduce interval to every other day or every third day. Max Maintenance Dose: 5mg/kg/day or 200mg/day
 
Short-Term Prophylaxis† (before a procedure) 2.5 to 10mg/kg/day. Administer 5 days before and 2-3 days after procedure.
	Danazol 50mg, 100mg, 200mg Capsule Danocrine 50mg, 100mg, 200mg Capsule
Tranexamic Acid	Cyklokapron Lysteda (Oral)		
Adults† 1g twice daily. Adjust dose as needed to between 0.25g and 1.5g twice daily. Max Dose: 3.9g/day
 
Pediatrics† 20mg/kg twice daily. Adjust dose as needed to between 10mg/kg twice daily and 25mg/kg three times daily.
	Lysteda 650mg Tablet Tranexamic Acid 650mg Tablet

Generic	Brand (Administration)	Acute Attack Dose	Long-Term Prophylaxis Dose	How Supplied
Aminocaproic Acid	Amicar (Oral)		
Adults† First Month: 16g per day, in divided doses every 4-6 hours. Maintenance Dose: 2g three times daily. Adjust dose as needed to between 1g twice daily and 4g three times daily. Max Dose: 36g/day
 
Pediatrics† 0.05g/kg twice daily. Adjust dose as needed to between 0.025g/kg twice daily and 0.1g/kg twice daily.
	
Amicar 0.25g/mL Oral Solution (236.5 ml bottle) Amicar 500mg, 1000mg Tablet Aminocaproic Acid 0.25g/mL Oral Solution (236.5 ml bottle) Aminocaproic Acid 500mg, 1000mg Tablet

Oxandrolone	Oxandrin (Oral)		
Adults† 10mg daily. Adjust dose as needed to between 2.5mg every three days and 20 mg daily.
 
Pediatrics† 0.1mg/kg daily. Adjust dose as needed to between 2.5mg weekly and 7.5mg daily.
	
Oxandrolone 2.5mg Tablet Oxandrolone 10mg Tablet

Methyltestosterone	Android Methitest Testred Virilon (Oral)		
Adult Men† 10mg once daily. Adjust dose as needed to between 5mg every three days and 30mg daily.
 
Not recommended in women and children
	
Android 10mg Capsule Methyltestosterone 10mg Capsule Testred 10mg Capsule Methitest 10mg Tablet

Generic	Brand (Administration)	Acute Attack Dose	Long-Term Prophylaxis Dose	How Supplied
Stanozolol	Winstrol (Oral)		Adults† 2mg daily. Adjust dose as needed to between 1mg daily and 6mg daily. Pediatrics† 0.5mg daily. Adjust dose as needed to between 0.5mg weekly and 2mg daily.	?

IU = International Units; IV = Intravenous Administration; SC = Subcutaneous Administration; SWFI = Sterile Water for Injection

† = Off-Label Indication; * = Brand-Name Only (Brand Exclusivity); ? = No results in pharmacy databases

Drugs Indicated Only for HAE: Cinryze, Haegarda, Berinert, Takhzyro, Ruconest, Kalbitor, Firazyr, Orladeyo

Annex 2: Variable definitions and code lists

Treatment - Brand Name (Generic)	J Codes and NDCs	Source
Takhzyro (lanadelumab)	J0593 Injection, lanadelumab-flyo, 1 mg (code may be used for Medicare when drug administered under direct supervision of a physician, not for use when drug is self-administered) NDCs: 47783-0644-01	Clinical Pharmacology Database²⁰ and HCPCS²¹
Haegarda (C1 Inhibitor)	J0599 - Injection, HAEGARDA, 10 units (effective Jan 1, 2019) NDCs: 63833-0828-02 63833-0829-02	Clinical Pharmacology Database²⁰ and HCPCS²¹
Cinryze (C1 Inhibitor)	J0598 - Injection, C1 esterase inhibitor (human), 10 units NDCs: 42227-0081-01 42227-0081-05	Clinical Pharmacology Database²⁰ and HCPCS²¹
Ruconest (C1 Esterase Inhibitor, Recombinant)	J0596 - Ruconest, 10 units NDCs: 68012-0350-01 68012-0350-02 71274-0350-01 71274-0350-02	Clinical Pharmacology Database²⁰ and HCPCS²¹
Kalbitor (ecallantide)	J1290 - Injection, ecallantide, 1 mg NDCs: 47783-0101-01	Clinical Pharmacology Database²⁰ and HCPCS²¹
Berinert (C1 Inhibitor)	J0597 - Injection, C1 Esterase Inhibitor (Human), BERINERT, 10 units NDCs: 63833-0825-02	Clinical Pharmacology Database²⁰ and HCPCS²¹
Firazyr (icatibant)	J1744 - Injection, icatibant, 1 mg NDCs: 00093-3066-19	Clinical Pharmacology Database²⁰

	00093-3066-34 00093-3066-93 24201-0207-01 24201-0207-03 54092-0135-01 54092-0135-02 54092-0702-02 54092-0702-03 60505-6214-01 63323-0574-01 63323-0574-86 63323-0574-93 69097-0664-34 69097-0664-68	and HCPCS²¹
Orladeyo (berotralstat)	Newly approved drug (December 2020) and not available in the analysis data set which runs through March 31st 2020.	
Danazol (Danocrine)	NDCs: 00527-1368-01 00527-1369-01 00527-1369-06 00527-1392-01 00555-0633-02 00555-0634-02 00555-0635-02 00555-0635-09 42291-0243-01	Clinical Pharmacology Database²⁰
Cykokapron Lysteda (Tranexamic Acid)	NDCs: 00591-3720-30 55566-2100-01 55566-2110-02 60505-3638-01 60505-3638-03 66993-0090-30 66993-0121-30 69918-0301-30	Clinical Pharmacology Database²⁰
Amicar (Aminocaproic Acid)	NDCs: 17478-0447-08 17478-0768-30 17478-0769-30 49411-0050-30 49411-0051-30 49411-0052-08	Clinical Pharmacology Database²⁰

	52817-0815-08 60219-1637-03 60687-0505-25 62559-0225-30 66689-0330-08 69238-1596-08 69680-0115-30 69680-0116-30 72205-0049-30	
Oxandrin (Oxandrolone)	NDCs: 49884-0301-01 00185-0271-01 49884-0302-02 00185-0272-60	Clinical Pharmacology Database²⁰
Android Methitest Testred Virilon (Methyltestosterone)	NDCs: 00187-0902-01 00115-1408-01 00187-0901-01 00115-7037-01	Clinical Pharmacology Database²⁰
Winstrol (Stanozolol)	NDCs: 0024-2253-04??	Clinical Pharmacology Database²⁰
Prophylactic use of Cinryze and Ruconest	Algorithm and code lists	Source
Cinryze prophylactic use	Cinryze is indicated for prophylaxis, but is used off-label for acute attacks. Prophylactic use will be defined as continuous refills of Cinryze averaging ≥ 1500 IU/week for ≥ 90 days.	Riedl 2018²²
Ruconest prophylactic use	Ruconest is indicated for on-demand use, but is used off-label for prophylaxis. Patients with Ruconest prophylactic use will be excluded from the cohort. Prophylaxis use will be defined as continuous refills of Ruconest averaging 50 IU/kg once weekly for 90 days.	Riedl 2018²²
every four-week	Used to determine if a dose reduction occurred.	

administration of Takhzyro	This will be measured over a 90-day follow-up period based on total dose <= 1200 mg over that period. The 1200 mg is based on three 300 mg injections plus one additional injection to account for potential variation in exact timing.	
Attack severity	Algorithm and code lists	Source
Severe	
ED visit with/without hospitalization, identified based on “Type of service” coded as inpatient or emergency room. Events identified as HAE-specific include at least one of the following diagnose (as a primary diagnosis for hospitalizations /or treatments indicative of an attack:
 
 € Codes often associated with HAE: ICD-9-CM 277.6 or ICD-10-CM D84.1 € Angioedema diagnosis: ICD-9-CM 995.1 or ICD-10-CM T78.3* € Administration of on-demand HAE treatment € Diagnosis of swelling, abdominal pain, or asphyxiation: 
 o ICD-9-CM 518.81, 518.84, 787.0*, 782.2, 789.0*, 786.02, 786.05, 786.1 o ICD-10-CM J96.0*, J96.2*, J96.9*, R06.0*, R06.1, R10.*, R11.*, R22.0*, R22.1, R19.0 	
UpToDate states severe attacks are treated in ED.²³
 
Tachdjian 2020¹
 
Zilberberg 2010²⁴
 
Longhurst & Bork, 2019

Non- severe attack	
Each dose of an on-demand therapy over two acute attack doses is considered an attack. The number of doses dispensed will be calculated from the quantity dispensed and recommended dose and
 
Any on-demand therapy administered outside an inpatient or emergency room setting will be considered a non-severe attack.
	
Utilization	Algorithm and code lists	Source
cricothyrotomy/ tracheotomy	emergency tracheotomy (31603) and an emergency cricothyrotomy (31605)	
Dillon 2013²⁵
 
Esposito²⁶

intubation	The appearance of any of the following encounters CPT - 31500 ICD10 - 09HN7BZ, 0DH57BZ, 0DH58BZ, 0WHQ73Z, 0WHQ7YZ, 09HN8BZ, 0B21XEZ, 0BH13EZ, 0BH17EZ, 0BH18EZ, 0CHY7BZ, 0CHY8BZ ICD9 - 96.04, 96.7x, 96, 96.0,96.5	Pandya 2019²⁷ Singh 2020²⁸ De novo code look up
artificial respiration	The appearance of any of the following encounters Invasive mechanical ventilation: CPT - 94002, 94003, 94004, 94005, E0472, K0534 ICD10 - 5A1935Z, 5A1945Z, 5A1955Z noninvasive ventilation: CPT - 94660, A7027, A7034, A7044, E0452, E0470, E0471, E0601, K0183, K0193, K0194, K0532, K0533 ICD10 - 5A09459, 5A09557, 5A09357, 5A09358, 5A09359, 5A0935B, 5A09457, 5A09458, 5A0945B, 5A09558, 5A09559, 5A0955B ICD9 - 93.90 ventilation NOS: CPT- 94656, 94657 ICD10 - 5A0920Z, 5A0945Z, 5A0955Z, 5A19054, 5A0935Z, 5A09358, 5A0935B,	Pandya 2019²⁷ Singh 2020²⁸ Rosenthal 2020²⁹ De novo code look up
Costs	Algorithm and code lists	Source
Home nurse treatment	Standard cost amount for medical service claims with an on-demand drug administration where the place of service is ‘home’	
Physician office visit	Standard cost amount for medical service claims with an on-demand drug administration where the place of service is ‘office’	
ED visit	Standard cost amount for medical service claims where the type of service is coded as ‘emergency room, professional or facility’	
Hospitalization	Standard cost amount for medical service claims where the type of service is coded as ‘acute inpatient facility’	

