5.1.1.2 Prophylaxis initiation cohort for evaluation

[figure not shown]
Patients will be eligible to enter the cohort on initiation of Takhzyro, Haegarda, or Cinryze as a prophylactic treatment during October 10, 2008 through October 3rd, 2019 (Figure 1). October 2008 was selected as the start of the study period based on the approval date for Cinryze, the earliest of the medications to be approved. Clinical experts confirmed that 2008 reflects the current treatment paradigm of medications targeting the BK pathway and that all new treatments after 2008 reflect a continual shift away from inferior anabolic androgen therapies. The study period was also selected to maximize sample size for this rare disease.

New use will be defined as no use of Takhzyro or Haegarda, during the 180 days prior (washout period), and no use of Cinryze as a prophylactic treatment during this 180-day washout period. Because Cinryze is used for both acute attacks (off label) and prophylaxis, patients will be excluded based on evidence of prophylactic use of Cinryze (see definition in Annex 2) during the 180 days prior to cohort entry and will be required to have continuous enrollment and evidence of recurring use during the 90 days following cohort entry. Patients receiving other prophylactic treatments (see Annex 1) during the baseline period will also be excluded. Each patient will be included only once, on the first qualifying event. Patients will be required to have at least 180 days of enrollment prior to cohort entry to obtain baseline attack rates.

Using this cohort, we will evaluate baseline outcomes. Patients' demographic characteristics will be assessed at cohort entry. Patients' attack rates, and attack-related medical service utilization and costs will be evaluated.

Note: HAE does not have specific ICD9/10 diagnostic codes. We used initiation of HAE specific treatment to identify patients of interest (i.e., patients with HAE). The method of using HAE treatments to identify HAE patients has been used widely in the literature (Tachdjian 2020, Banerji 2020, [Vande Walle 2018](#)).¹⁻³ In addition, there is no indication that HAE treatments are used off-label for non-HAE patients.

Figure 1: Prophylaxis initiation cohort study design diagram

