5.3.1.1 Optum's De-identified Clinformatics® Data Mart

Optum's Clinformatics® Data Mart (CDM) is derived from a database of administrative health claims for members of large commercial and Medicare Advantage health plans. The database includes approximately 17-19 million annual covered lives, for a total of over 65 million unique lives over a 9-year period (1/2007 through 12/2019). Clinformatics® Data Mart is statistically de-identified under the Expert Determination method consistent with HIPAA and managed according to Optum® customer data use agreements.^{8,9} CDM administrative claims submitted for payment by providers and pharmacies are verified, adjudicated and de-identified prior to inclusion. This data, including patient-level enrollment information, is derived from claims submitted for all medical and pharmacy health care services with information related to health care costs and resource utilization. The population is geographically diverse, spanning all 50 states.

There are 67,691,644 total patients in the data with events spanned January 1, 2007 through March 31, 2020.

Please see Annex 4 for HAE drug coverage policies for United Healthcare.

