5.4 Statistical analysis

5.4.1.1 Baseline attack rates (primary objective)

Attack rates will be calculated as the total number of attacks in the cohort divided by the number of person-months during baseline (six months prior to initiation of prophylaxis treatment). The rates

and percentages of attacks by severity (severe all-cause, severe-HAE specific, non-severe) will also be calculated for the baseline cohort.

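### Haegarda billed medically before 2019 without a listed NDC may escape the 180-day washout, so some entrants up to 29 June 2019 may not be new users

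*Protocol*

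**What the plan says.** Section 5.2 of the protocol sends the reader to Annex 2 for every variable definition, so the drug code lists are fixed there. The Haegarda row holds two kinds of identifier:

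- one procedure code with a start date: "J0599 - Injection, HAEGARDA, 10 units (effective Jan 1, 2019");
- two product codes with no date and no stated claim type: "NDCs: 63833-0828-02 63833-0829-02".

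The row gives no miscellaneous code, no predecessor code and no rule for medical claims before 2019. The Cinryze row lists "J0598 - Injection, C1 esterase inhibitor (human), 10 units", a descriptor that names no brand.

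Section 5.1.1.2 sets the new-user rule: "New use will be defined as no use of Takhzyro or Haegarda, during the 180 days prior (washout period"). Cohort entry runs over "October 10, 2008 through October 3rd, 2019". The primary estimator in section 5.4.1.1 uses the six months before initiation: "Attack rates will be calculated as the total number of attacks in the cohort divided by the number of person-months during baseline". Section 5.3.1.1 describes the data as "derived from claims submitted for all medical and pharmacy health care services".

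**The concern.** The washout can only exclude use that the code list can see. Haegarda was one of the three therapies in the November 2018 review (sections 4 and 5.2.1.2), and section 5.1.1.3 ties the one-year follow-up cap to how recently Takhzyro was approved. Together these strongly imply that Haegarda was in use before J0599 existed. The protocol lists J-codes for the injectable HAE products, so it expects some of this use on medical claims.

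Take a patient whose Haegarda was billed medically during 2018 on claims without a listed NDC. None of those claims matches Annex 2. The first J0599 claim in 2019 then looks like initiation after a clean washout, although the patient was already on prophylaxis. The same patient, on moving to Takhzyro or Cinryze, could pass as free of Haegarda.

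At stake is the primary baseline attack rate, which is meant to describe patients before prophylaxis and to inform the cost-effectiveness model. Section 4 says that small changes in attack frequency could alter the model's conclusions substantially, and section 5.4.1.3 calls the sample small. Treated time counted as baseline would be expected to lower the rate. For such patients, the exploratory follow-up would also begin part-way through treatment.

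**Working it through.** The protocol states no figure on this point, so there is nothing to reproduce. The check is date arithmetic and a side-by-side reading of the code list.

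**Inputs.** J0599 starts 1 January 2019 (Annex 2). The washout is 180 days and entry runs from 10 October 2008 to 3 October 2019, 4,011 days inclusive (section 5.1.1.2). Takhzyro was approved on 23 August 2018 (section 5.1.1.4).

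**Washout days before the code existed.** For index date d:

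max(0, min(180, 1 Jan 2019 − (d − 180 days)))

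| Index date | Days before J0599 | Share of 180 |
|---|---|---|
| 1 Jan 2019 | 180 | 100% |
| 15 Jan 2019 | 166 | 92% |
| 1 Feb 2019 | 149 | 83% |
| 1 Apr 2019 | 90 | 50% |
| 1 Jun 2019 | 29 | 16% |
| 29 Jun 2019 | 1 | 0.6% |
| 30 Jun 2019 | 0 | 0% |

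From 30 June 2019 the whole washout lies within the life of the code.

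**Length of the exposed window.**

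- Entry on J0599: 1 January to 3 October 2019 is 276 days. Of these, 180 (65%) have a washout reaching back before the code and 96 do not. Against the full entry window, 180/4,011 = 4.5%.
- Entry on Takhzyro after unseen Haegarda: 23 August 2018 to 29 June 2019 is 311 days, and 311/4,011 = 7.8%.
- Entry on Cinryze after unseen Haegarda: the window also closes on 29 June 2019. Its start depends on when Haegarda came into use, which the protocol does not give.

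These are shares of calendar days, not of patients. A continuing user would normally surface at the earliest J0599 billing of 2019, so such entries would cluster early in the window, where nearly all of the washout is uncovered.

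**What each route leaves visible.**

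| Haegarda before 2019 | Seen by Annex 2? |
|---|---|
| Pharmacy claim with a listed NDC | Yes, at any date |
| Medical claim with a listed NDC | Yes, if NDCs are searched on medical claims; the protocol does not say |
| Medical claim, no NDC, billed under J0598 | Seen, but as Cinryze |
| Medical claim, no NDC, any other code | No |

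**The J0598 case.** Annex 1 gives the Haegarda regimen as "60 IU/kg twice weekly (every 3-4 days"). At the prior-review mean female weight in Annex 3 Table 1 (76.4, taken as kg), 60 × 76.4 × 2 = 9,168 IU per week. The Annex 2 threshold for prophylactic Cinryze is an average of 1,500 IU per week over at least 90 days. Sustained Haegarda billed under J0598 would therefore meet that threshold and be caught by the Cinryze washout. It could also be counted earlier as a Cinryze initiation.

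**Direction and ceiling of the bias.** Let f be the share of baseline person-time that is hidden on-treatment time, and r the proportional reduction in attacks on prophylaxis. If hidden users would have had the same untreated rate λ as the others, the observed rate is λ(1 − f·r). The proportional loss f·r cannot exceed f. The protocol gives neither f nor r, so no percentage follows.

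**The case against.** The strongest answer is that the gap may be empty. The Haegarda row lists two NDCs with no date limit and no restriction to pharmacy claims, and the data hold both claim types. Haegarda is subcutaneous and given twice weekly (Annex 1), and section 5.3.1.2 treats pharmacy dispensing as the usual gold standard for exposure. Dispensing under an NDC may well be the main channel, and there the washout works. Nothing in the protocol shows that any Haegarda was billed medically without an NDC before 2019. If it went under J0598, sustained use would have been excluded as Cinryze prophylaxis. This stands, and it limits the point to a conditional one.

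A reader might infer that medical Haegarda can be found only by J0599 and that established users do enter as new. The documents support neither statement. The NDCs may also be matched on medical claims, and the protocol has no data on how Haegarda was billed.

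It can also be said that the claim types searched for an NDC are a programming detail, and that the follow-up analysis is exploratory and not a direct model input (section 5.1.1.3). The second is fair, and the weight of the point rests on the baseline rate. The first only partly answers it: searching NDCs on medical claims cannot find claims that carry none, and Annex 2, where the definitions are fixed, has no rule for those.

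**Conclusion.** The point holds in conditional form. As written, a J0599 claim dated 1 January to 29 June 2019 that is a patient's first Haegarda evidence does not establish new use, because some or all of its washout predates the code. The absence of Haegarda evidence is open to the same doubt for Takhzyro and Cinryze initiators before 30 June 2019. Any resulting error would be expected to lower the primary baseline rate, provided that prophylaxis reduces attacks and hidden users resemble the rest of the cohort.

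The size is unknown. It depends on how many patients had medical-only Haegarda with no listed NDC, outside J0598, continuing into 2019. A reader might want a percentage effect on the rate, but any such figure would only restate an assumed share of hidden users. Nor can the point be extended to other J-codes in Annex 2: Haegarda's is the only one for which the protocol gives an effective date. The gap is also limited in time and closes on 30 June 2019.

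**What to change.** 1. State in Annex 2 that the two Haegarda NDCs are applied to medical as well as pharmacy claims. If this is already the intention, only the wording changes.
2. Do not accept a J0599 claim dated 1 January to 29 June 2019 as the first qualifying event when it is the patient's first Haegarda evidence. At minimum, report the primary baseline attack rate with and without these patients.
3. Check J0598 claims from before 2019 for possible Haegarda use, both among these entrants and among Takhzyro and Cinryze initiators before 30 June 2019.

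Step 1 alone is not enough, because it finds only claims that carry an NDC; step 2 covers J0599 entrants whose earlier claims carry none. For Takhzyro and Cinryze initiators, use billed with no NDC and outside J0598 would stay unseen, and this should be stated as a limitation. The cost is a sentence in the code list, a date condition, a claims check and the loss of a few early-2019 entrants identified by J-code alone. Some of those may be genuine initiators, which is the reason to allow the with-and-without report as the lesser option.

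### The flat Cinryze prophylaxis cut in Annex 2 is not met by Annex 1's standard 6-11-year schedule or by courses under 90 days, and the same rule decides the washout

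*Protocol*

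**What the plan says.** Annex 2 (prophylactic use of Cinryze and Ruconest) gives a single Cinryze rule: "Prophylactic use will be defined as continuous refills of Cinryze averaging ≥ 1500 IU/week for ≥ 90 days". The Ruconest rule in the next row is set per kilogram; the Cinryze rule depends on neither weight nor age.

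Annex 1 lists two Cinryze prophylaxis schedules. One is "Adults & Children ≥12 years 1,000 units every 3-4 days". The other is "Children (6-11 years) 500 units every 3-4 days Max Dose: 1,000 units every 3 days".

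Section 5.1.1.2 sets no age limit. New use requires "no use of Cinryze as a prophylactic treatment during this 180-day washout period", and the exclusion points to the Annex 2 rule: "patients will be excluded based on evidence of prophylactic use of Cinryze (see definition in Annex 2) during the 180 days prior to cohort entry". By contrast, any use of Takhzyro or Haegarda in those 180 days excludes the patient. Cinryze initiators must also show "evidence of recurring use during the 90 days following cohort entry"; neither that sentence nor Section 5.1.1.3 gives a weekly amount.

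Section 5.4.1.1 computes the primary attack rate over the six months before prophylaxis starts, pooling attacks over person-months.

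**The concern.** One rule does two jobs that pull in opposite directions. When it confirms that a Cinryze start is prophylactic, it should be strict, because Cinryze is also used off label for acute attacks. When it screens out previous prophylaxis, strictness lets treated patients through. The cut also appears to suit the schedule from age 12 and not the one listed for ages 6-11.

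At stake is the meaning of the primary output, an attack rate before prophylaxis. Section 4 says that cost-effectiveness is sensitive to attack frequency, and Section 5.4.1.3 describes the sample as small, so a few misclassified patients could matter. Switching among the three drugs is something the protocol itself plans to measure, and Annex 1 lists Haegarda from age 6, so a route from Cinryze into the cohort exists.

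**Working it through.** **Inputs.** Cut of 1,500 IU/week for 90 days (Annex 2); schedules from Annex 1; 180-day washout (Section 5.1.1.2); prior base-case rate of 3.39 attacks/month (Annex 3, Table 2). Units and IU are taken as equivalent. The protocol attributes the 1,500 figure to a cited source and does not derive it, so only its consistency with Annex 1 can be checked.

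**Weekly amount = dose × 7 / interval in days**

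| Annex 1 schedule | Calculation | IU/week | Share of 1,500 | Rule met? |
|---|---|---|---|---|
| 6-11 years, standard, every 4 days | 500 × 7/4 | 875 | 58% | No |
| 6-11 years, standard, every 3 days | 500 × 7/3 | 1,167 | 78% | No |
| 6-11 years, maximum | 1,000 × 7/3 | 2,333 | 156% | Yes |
| 12 years and over, every 4 days | 1,000 × 7/4 | 1,750 | 117% | Yes |
| 12 years and over, every 3 days | 1,000 × 7/3 | 2,333 | 156% | Yes |

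Over 90 days the rule needs 1,500 × 90/7 = 19,286 IU. The standard 6-11 schedule supplies 500 × 90/4 = 11,250 to 500 × 90/3 = 15,000, so it fails even with perfect adherence.

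**Treated time that can pass the washout.** From age 12, a regular course of up to 89 days does not reach the duration: 89/180 = 49% of the window. For a child on the standard schedule the amount is never reached, so all 180 days (100%) can be treated.

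**If the unflagged Cinryze is ignored.** With an assumed reduction e in attacks on Cinryze and a treated share f, the observed rate is 3.39 × (1 − f × e). No document gives e; take 30-70%.

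- f = 89/180: 3.39 × (1 − 0.494 × 0.3) = 2.89, down to 3.39 × (1 − 0.494 × 0.7) = 2.22 attacks/month.
- f = 1: 3.39 × 0.7 = 2.37, down to 3.39 × 0.3 = 1.02 attacks/month.

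**If it is counted as on-demand.** Annex 2 counts each on-demand dose beyond two as an attack. Taking 1,000 units as one acute dose (Annex 1, adults), 89 days give 89/4 to 89/3, about 22-29 doses. That makes 20-27 spurious attacks over six months, or 3.3-4.5 per month.

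Both illustrations describe a single affected patient, not the cohort.

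**The case against.** **The rule can be met at ages 6-11, and older children are unaffected.** This stands. The maximum in the same Annex 1 cell clears the cut, as does the schedule from age 12. A reader might infer that the rule loses children in general; the documents support this only for ages 6-11 on the standard schedule.

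**Loss of young Cinryze initiators is not stated.** This also stands. The requirement after entry is recurring use with no weekly figure, and the footnote to Annex 3, Table 3 describes it as adherence. Applying the Annex 2 rule there is the likely reading, since the protocol has no other definition, but it is an inference. On the looser reading a child could enter at Cinryze initiation and, because each patient enters once, could not re-enter on Haegarda. That closes the gap for that child, but not for one whose Cinryze began too early to leave 180 days of enrolment before it.

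**Another exclusion may catch these patients.** Section 5.1.1.2 adds: "Patients receiving other prophylactic treatments (see Annex 1) during the baseline period will also be excluded". Cinryze has its own rule in the sentence before, so this does not clearly reach it.

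**The 90 days are deliberate.** They separate prophylaxis from acute use, and it is tempting to conclude that they should simply be dropped from the washout. The figures do not support that. At 3.39 attacks/month (0.78 per week) and one or two acute doses of 1,000 units, acute use alone is about 780-1,560 IU/week. A washout on amount without duration could remove frequent attackers preferentially and itself lower the baseline rate.

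**The direction of bias is open.** A reader might infer that the baseline rate is necessarily too low. Section 5.2.1.2 and Table 2 do not list Cinryze as on-demand, which favours that reading, but Section 5.1.1.2 and Annex 2 describe its off-label acute use. How unflagged Cinryze enters the attack count is not settled.

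**Conclusion.** The point holds in a limited form. The Annex 2 rule is inconsistent with Annex 1's standard 6-11-year schedule, which reaches only 58-78% of the cut. Because the washout uses the same rule, that schedule for any duration, or regular Cinryze of up to 89 days at any age, does not exclude a patient. Such a patient can start Haegarda, or Takhzyro from age 12, as a new user with treated time in the primary baseline rate. If recurring use means the Annex 2 rule, 6-11-year-olds on the standard schedule are also lost as Cinryze initiators.

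The sign of the error depends on whether the unflagged Cinryze is ignored (rate too low) or counted as on-demand (rate too high). The effect on the pooled rate cannot be computed, because the documents do not give the number of such patients; it may be small, and the prior model's mean age of 39.63 suggests few will be aged 6-11. Section 5.1.1.2 also does not say whether the 90-day run must lie wholly inside the 180 days, which affects who is caught.

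**What to change.** 1. Reconcile Section 5.1.1.2, Annex 1 and Annex 2 by making the Cinryze detection cut age-specific, in the proportion it already bears to the lower figure from age 12: 1,500/1,750 = 0.857, and 0.857 × 875 = 750 IU/week for ages 6-11. This is a threshold for classifying claims, not a dose. It gives both age groups the same margin for missed fills on the four-day interval. How well it separates prophylactic from acute use at that age is untested.
2. State that the same cut governs recurring use after entry, in Sections 5.1.1.2 and 5.1.1.3.
3. Keep the 90-day rule for the main washout, and say whether the run must fall wholly within the 180 days and how Cinryze that does not meet the rule enters the attack count.
4. Add to Section 5.4.1.4 a sensitivity analysis of the baseline attack rate that excludes patients with any (or repeated) Cinryze fills in the 180 days before entry.

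The cost is a few lines of text and one further run. The sensitivity analysis will have slightly fewer patients and will drop some frequent acute users of Cinryze, so it should sit beside the main washout and not replace it.
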